## Recruitment

Participant recruitment will be coordinated in conjunction with the OAIC Clinical Research Core. Potential participants will be recruited from the general population in the North/Central Florida region through:

- IRB-approved advertisements (postcards, brochures, social media, newspaper ads) providing basic information about the study and inviting potential participants to call for additional information;
- Contact of potential participants who are enrolled in the Claude D. Pepper Recruitment Registry (IRB#417-2007) by Registry staff;
- We will also use existing entities of UF Health that include the Consent2Share program. Individuals who screen out of other studies may also be approached and asked about their interest in this study;

## Screening process

We will employ a staged screening process where we will verify eligible participants over a series of contacts.

- Interested participants are first screened by phone. The phone interview is designed to exclude individuals who are ineligible due to safety concerns or not interested after learning about the study.
- After the phone screening, at the first in-person screening visit, we will consent participants with a short form and perform the SPPB test. Participant with SPPB score of ≤ 8 will be invited for the baseline visit.

## Interventions

**Resistance Training Intervention:** The 14-week supervised resistance training intervention will include a full body, resistance training performed three days per week. The intensity, volume, tempo, and progression will be based on the Federal Physical Activity guidelines as shown in Table 2.

Exercises: The resistance training exercises will include mainly multi-joint exercises using selectorized machines to minimize training duration and maximize the benefit. Each session will include upper body exercises (Chest Press, Shoulder Press, Seated Rows) and lower body exercises (Leg Press, Leg Extension and Leg Curls, and Calf raise) that will be tailored to the participant needs. Interventionists will supervise all exercise sessions.

Warm up & cool down: Each training session will begin with 1 set of warm-up at a lighter load for 8–10 repetitions on 1 multi-joint upper body and 1 lower body machine. Each session will end with a 5 min cool-down involving stretching exercises and light calisthenics

Preparatory phase: Considering the participants are low functioning; we will use a 2-week *preparatory phase*, which will ensure sufficient time for connective tissue adaptations and for the participants to learn proper lifting form and breathing technique.

Training Phase: The training phase will last for 12 weeks and will be divided into 2 phases as shown in Table 2.

Intensity: The intensity will be maintained at 6-8 (moderate to vigorous RPE) as recommended by ACSM for older adults and the sets will be done until volitional fatigue. The CR-10 BORG's scale ranges from 1-10 will be used to document perceived exertion during resistance training.

Progression: The load will increase when participants can perform all repetitions in all sets .

Table 2. Resistance training parameters		
Preparatory Phase		Training Phase
	Week 1-2	Week 3-5
Days/wk	3	3
Sets * Reps	1-2* 12-15	3 *12-15
RPE	6 - 8	6 - 8
Rest (min)	1	1
Progression		Can do 3 sets of 15
		Can do 3 sets of 10

Note: All values are subject to change based on participant availability and ability of the participant to conduct the number of sets and reps prescribed.

**Successful Aging:** The comparator group will meet every 2 weeks. Weekly workshops will include flexibility exercises and presentation topics related to older adults, such as preventive services and screenings, finding credible health information, and so forth. We instruct all control participants not to change their PA levels and the importance of remaining weight stable throughout the study period. The rationale for the health education group in place of a sedentary control is to minimize the social interaction effects and to minimize participant drop-outs.

**Tampa Scale for Kinesiophobia (TSK)** – The TSK is a reliable and valid self-report checklist that uses a 4-point scale to measure of fear of movement or (re)injury. The scale is based on the model of fear avoidance, fear of work related activities, fear of movement and fear of re-injury. The TSK is considered as one of the most suited questionnaires to evaluate pain beliefs and fear of movement/(re) injury in chronic low back pain.

**Borg Category Ratio (CR) 10 pain/RPE scale** – The Borg CR10 pain/RPE scale is a reliable, valid, and frequently used quantitative measure of perceived exertion and pain during each exercise session and after the physical function tests. The Borg CR10 uses a category ratio scale that ranges from 0 (no pain/exertion) to 10 (maximal pain/exertion).

**Gait Analysis:** We will ask participants to walk at their usual pace and a rapid pace two times across a carpet that contains sensors arranged in a grid pattern (48 X 288) (GAITRite Inc.). The system collects temporal (step time, gait cycle, single support time, double support time, stance time and swing time) and spatial (step length and stride length) parameters.

**Vital signs:** During screening, resting blood pressure and heart rate, height, weight will be measured. Blood pressure and heart rate are measured to assess eligibility criteria and for safety purposes and others are collected for descriptive purposes.

**Oxygen Consumption:** Oxygen consumption will be measured using a portable metabolic unit (Cosmed K4b2) for three daily tasks for 6 minutes each. Oxygen consumption will be measured breath-by-breath through a mask that is fitted to the participants face.

Mopping: Mop a 200 sqft room using mop and water  
Lifting: Lift chairs and transfer across a 200 sq ft room

### **Muscle mass measurements:**

- **D3-Cr method:** The participant will ingest a 60-mg dose of deuterated creatine (D3-Cr), a non-radioactive isotope, at the baseline assessment. They will return morning to provide a urine sample 3-5 days later. The sample will be frozen and deidentified for D3-creatinine analysis. urine samples (-20°) will be shipped to University of California, Berkeley where unlabeled creatinine and creatine will be measured using high-performance liquid chromatography(HPLC) and mass spectrometry (MS). The details of methods have been published previously.
- **DEXA:** Total and regional body composition will be measured using at UF site Dual-energy X-ray absorptiometry (DEXA, QDR-4500w; Hologic, Waltham, MA, USA). DEXA is widely used in trials, is safe and is currently recommended to diagnose sarcopenia.

**Walk Tests:** The 400m walk test is a feasible, objective, reliable, well-validated and used in large clinical trial. Participants will be asked to walk 400 m at their usual pace, without overexerting, on a 20-m course for 10 laps (40 m/lap). The 6 min walk test will include walking at a rapid pace around 2 cones 20 m apart wearing the portable metabolic unit.

**Physical performance** will be measured using the Short Physical Performance Battery (SPPB), which is based on a timed 4-m walk, balance, and chair stand tests. This scale is reliable and valid for predicting institutionalization, mortality and disability. The score ranges from 0 (worst performers) to 12 (best performers).

**Muscle strength** will be measured using tests of isometric grip strength and isokinetic leg extension test. Grip strength is frequently used of upper body skeletal muscle function and has been widely used as a general indicator of functional status. Grip strength will be measured using the Jamar dynamometer. Leg strength will be assessed using Isokinetic dynamometry (System 3 pro; Biodex Medical Systems, Shirley, NY, USA) at velocities of 60° and 120° per second.

Participants will perform 2 sets of 5 maximal isokinetic leg extensions at each velocity with one-minute of rest between each set for the dominant leg.

**Dynamic balance** will be measured using the Timed Up and Go test which is widely used to examine mobility and dynamic balance. Also, the test is recommended as a screening test for falls by the American Geriatric Society and the British Geriatric Society. Standing or static balance (narrow, tandem and semi-tandem) will also be assessed as part of the SPPPB test.

### **Adherence**

Adherence involves both attendance to scheduled sessions as well as the quality of the training that occurs during each session. Adherence to the exercise protocols are affected by personal, social and environmental factors. At a personal level, it is important to ensure that the goals of each participant are realistic. We recognize that social interactions between staff and participant as well as the broader social environment surrounding the study influence adherence. All staff will be instructed to engage with and be supportive toward all participants. We will also adopt a number of other strategies to improve attendance and quality of training sessions. Some strategies include, having trained interventionists to supervise training, including a preparatory phase to educate the participants about proper lifting technique, tailoring the training program based on the physical needs of the participant, maintaining a workout log to help motivation, monitoring missed visits so that the study coordinator can take prompt action and so forth

The physical environment and accessibility influence adherence. This includes such factors as ease of parking, transportation, and accommodations made for friends or significant others who may come to

training facilities to support participants via transportation, etc. At the time of baseline assessments, staff discuss these topics with each participant to be certain there are no significant barriers in this domain and/or to problem solve potential challenges that exist.

The comparator group will not participate in a resistance training intervention and hence pose a greater risk of dropping out. We expect, based on our previous experiences, that the flexibility exercises and health education classes offered every 2 weeks will serve an effective “active control” that will help to promote retention in the study. We will also provide an exercise prescription and education materials at the end of the study duration so that they can start a resistance training program outside the site.

## Retention

The following guidelines promote compliance to the protocol and retention

- Participant-staff relationship. A key element contributing to participants' continued commitment to the study involves fostering positive, respectful relationships between study participants and individual members of the staff.
- Continuity of care. In general, participants' appointments should be scheduled so that they can be seen by the same clinic staff members during each visit.
- Clinic environment. A clinic environment that is warm and pleasant, and oriented to the comfort of the participant.
- Participant-staff communications. Good and consistent communication is essential. Instructions are clear and interactions are friendly and individualized. The participant is reminded of the benefits of study participation. Written reminders about appointments further enhance communication efforts.
- Convenience and accessibility. An easily accessible clinic location, availability of transportation, and convenient clinic hours all serve to facilitate study adherence. We will make study visits as easy as possible for participants, a critical factor to the success of the study. All sites take steps to ensure that clinic attendance is not compromised by a lack of transportation, unsuitable hours of clinic operation, or any similar circumstance. If necessary, participants are reimbursed for or are provided transportation to the clinic assessment visits.
- Time in clinic. Total clinic visit time is kept to a minimum, consistent with maintaining quality. If waiting is necessary, the situation is explained to the participant and, if possible, an offer is made for the participant to see another staff member, or to reschedule the visit. On the other hand, participants are not rushed or made to feel unwelcome. Study personnel trained to take time to visit with participants.
- Appointment reminders. Appointment reminders are used to prompt participants to come for clinic visits. These written reminders are mailed to participants so that they receive them before their scheduled visit date.
- Compensation: Participant will be compensated \$100.00 for being in the study. The remuneration is given for attendance at clinic assessments, regardless of the level of participation in intervention activities

## Statistical plan

Data analysis will be conducted at the Biostatistics and Data Management Core under the direction of [name]. Our primary analysis will use an intention to treat approach in which participants are grouped according to randomization assignment without consideration of their adherence to the exercise or successful aging health education programs. We will also perform “per protocol” analyses to examine muscle adaptations in those individuals with adherence rates > 80%.

Although pilot studies are not powered for hypothesis testing, we will use a mixed effects model to assess changes in the outcomes with baseline measure serving as covariate. Associations between muscle mass and other outcomes will be explored using a correlational analysis

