## 1. ABSTRACT

---

Muscle loss with age is considered to be an important cause of disability in older adults. However, current tools frequently used and recommended to measure muscle mass in trials have limitations: For example, DEXA (Dual-energy X-ray absorptiometry) and BIA (Bioelectrical impedance analysis)- both widely used in clinical trials cannot distinguish muscle tissue from non-muscle elements such as subcutaneous and intramuscular fat, skin, water and connective tissue

Deuterated creatine (D3Cr) dilution is a novel promising method that provides an accurate measure of the functional contractile tissue, without including the non-contractile elements, by measuring total body creatine. Our preliminary cross-sectional results in men aged >65 years show functional muscle mass (FMM) assessed by D3-Cr to be significantly associated with performance outcomes (SPPB, 400m walk, and chair stands) and long-term outcomes (incident mobility problems, serious injurious falls), while DEXA showed no associations. However, these are observational data and cannot determine a causative role of muscle per se on functional outcomes.

Hence, the objective of the pilot study is to assess the feasibility of our proposed future study to evaluate the role of muscle mass on functional outcomes. Specifically, the pilot study will randomize moderate to low-functioning older adults to a resistance training program or successful aging program to assess recruitment yields, participant adherence, retention, training program design aspects, sample size, and the cost of the main trial. Further, the impact of these changes in FMM on short-term performance outcomes, such as strength, walking speed, SPPB, self-reported measures, and balance will be examined.

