### 3. SPECIFIC AIMS / OBJECTIVES

#### Primary objective

- To evaluate the feasibility of implementing the D3Cr method in a resistance training trial as it relates to participant adherence, retention, training program design aspects (intensity, volume, frequency & safety) sample size, and cost of the main study.

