### **Temporary Exclusion Criteria**

A person meeting any of the following temporary exclusion criteria at the time of screening will not be enrolled but may be re-screened later.

- Recent bacterial/viral infection (e.g. pneumonia) (< 2 weeks);
- Acute febrile illness in past 2 months;
- Severe hypertension, e.g., SBP > 200 mm Hg, DBP > 110 mm Hg
- Major surgery or fracture or hip/knee replacement (< 6 months);
- Hospitalization within the last 6 months ( Not ER visits)

**Premature Withdrawal from the Study:** A participant has the right to withdraw from the study at any time, for any reason, and without repercussion. The investigators have the right to withdraw a participant from the study in the event of an intercurrent illness, AE, treatment failure, protocol deviation, and for administrative, or other reasons. An excessive rate of withdrawals would render the study uninterpretable; therefore, unnecessary withdrawal of participants should be avoided.

**Sample Size:** Our goal is to enroll a total of 24 participants. Since studies looking at changes in functional muscle mass in response to resistance training are not available, the sample size was arrived based on budgetary constraints and minimum number of participants required to meet feasibility goals. Assuming a conservative 20% loss to follow up, we estimate 12 participants per group (10 evaluable participants after the 20% loss due to attrition) would inform variance of the outcomes and feasibility for powering a future large-scale RCT.

**Randomization:** Randomization will be executed via a computer algorithm using random block lengths and stratified by gender. To ensure concealment of the allocation, the randomization procedures will be performed by an investigator who are not involved in the assessments

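### Must the plan fix the denominator of its 80% adherence rule and list separate analyses for the feasibility objective?

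*Combined protocol and SAP*

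**What the plan says.** The Statistical plan makes intention to treat the primary approach, grouping participants as randomized whatever their adherence. It adds a per-protocol analysis "to examine muscle adaptations in those individuals with adherence rates > 80" per cent. For the outcomes, "we will use a mixed effects model to assess changes in the outcomes with baseline measure serving as covariate"; correlations between muscle mass and the other outcomes are exploratory.

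The Adherence section describes the concept but gives no formula: "Adherence involves both attendance to scheduled sessions as well as the quality of the training that occurs during each session".

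The Interventions section sets the nominal programme: "The 14-week supervised resistance training intervention will include a full body, resistance training performed three days per week". The note under Table 2, which has a row for days per week, adds: "All values are subject to change based on participant availability and ability of the participant to conduct the number of sets and reps prescribed".

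The primary objective is feasibility. It covers adherence and retention, then "training program design aspects (intensity, volume, frequency & safety) sample size, and cost of the main study". The Abstract states the purpose as "to assess recruitment yields, participant adherence, retention, training program design aspects, sample size, and the cost of the main trial". The Sample Size paragraph rests the 24 participants on "budgetary constraints and minimum number of participants required to meet feasibility goals".

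**The concern.** Read together, these passages leave the adherence rate without a fixed denominator. If a schedule may shrink to suit a participant, and adherence is measured against what remains, someone who never trained three days a week could still count as fully adherent. Adherence is part of the primary objective, so the programme might look deliverable by construction. The per-protocol estimate would also pool people who had received quite different amounts of training.

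The second worry is wider. The analyses named in the Statistical plan serve mainly the secondary objectives (change over time and correlation). The section does not say how recruitment, retention, training delivered or cost will be summarised, and the feasibility goals mentioned under Sample Size are not listed. A reader could conclude that the primary objective has no analysis.

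**Working it through.** **The plan's own figure.** Sample Size gives 12 per group and 20% loss: 12 × 0.80 = 9.6, rounded to the stated 10 evaluable. It reproduces, and the adherence definition does not affect it.

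**Inputs.** 14 weeks, of which 2 are preparatory and 12 are training, at 3 days per week (Interventions); cut-off above 80% (Statistical plan); 12 participants in the resistance arm. The documents state no session total; 14 × 3 = 42 is inferred.

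**Individual level.** The lowest passing attendance is the smallest whole number above 0.8 × the denominator. Both reduced schedules are assumptions.

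| Schedule | Sessions | Share of 42 if all attended | Lowest attendance above 80% of schedule | That attendance as share of 42 |
|---|---|---|---|---|
| 3 days throughout | 42 | 100% | 34 (0.8 × 42 = 33.6) | 81.0% |
| 3 days for 2 weeks, then 2 days for 12 | 6 + 24 = 30 | 71.4% | 25 (0.8 × 30 = 24) | 59.5% |
| 2 days throughout | 28 | 66.7% | 23 (0.8 × 28 = 22.4) | 54.8% |

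**Arm level.** The documents do not say how many schedules would change. Assume that *k* of 12 move to two days throughout, that everyone attends every scheduled session, and that nobody drops out. On the changed schedules, 12/12 exceed 80% (exact 95% CI 74–100%). On 42 sessions, (12 − *k*)/12 do: 11/12, 10/12, 9/12 and 8/12 for *k* = 1 to 4; the last is 67% (CI 35–90%). Mean attendance against 42 is [(12 − *k*) + *k* × 28/42]/12, which is 97%, 94%, 92% and 89%. These scenarios show the most the choice of denominator can do for a given *k*, since they set aside the 20% loss that the plan expects.

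**What the arithmetic depends on.** It needs three readings that no passage states: that the Table 2 note covers a lasting cut in days rather than moved sessions or fewer sets; that scheduled sessions means those left after the cut; and that attendance alone decides adherence. The third conflicts with the Adherence section, which counts quality as well.

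**Comparator.** The Successful Aging section gives both a fortnightly and a weekly frequency; the Adherence section gives the fortnightly one. Over 14 weeks that is 7 or 14 sessions. Passing needs 6 of 7 (0.8 × 7 = 5.6) or 12 of 14 (0.8 × 14 = 11.2), and 6/7 = 12/14 = 85.7%. Once the sessions actually held are counted, the ambiguity has no effect on the rule. The wording is close to a clerical slip, for the sponsor to reconcile.

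**Feasibility items against the text.** The outcome analyses can supply the variance that Sample Size says will help to power the main trial, which covers the sample-size item. Safety has collection and reporting rules under adverse events. Recruitment, retention, adherence, training delivered and cost remain; these are counts, proportions and sums that need no model.

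**The case for a change.** The strongest case for a change is that adherence belongs to the primary objective, the text does not define it, and a few sentences would settle it. With the denominator open, it could be chosen after the data are seen. Nor is 42 self-evident, because the Adherence section refers to scheduled sessions and Table 2 may be altered. A bare ratio of attended to scheduled sessions could not show that three days a week was unattainable, which is something the main trial needs to know.

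Part of this stands. The formula is unwritten, the feasibility goals are unlisted, and the feasibility summaries are mostly left to the analyst. But no passage says that one ratio will be the only report. Frequency and volume are themselves named items of the primary objective, so a move to fewer days has to appear as a finding in its own right, whatever the adherence ratio shows.

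Fixing the per-protocol cut-off at 42 sessions is also open to challenge. The protocol expressly permits modified training, so someone who followed a permitted modification has not departed from it. Such a rule would exclude that person, drop the quality component, and leave comparator participants without a formula, although the 80% rule is not confined to the resistance arm.

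**Conclusion.** No change follows. The gap is a definition and some descriptive reporting that analysts of a 24-person pilot would fill sensibly, for example by giving attendance against both the planned and the modified schedule and noting how many schedules were modified.

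The size depends on assumptions. For one participant assumed to train two days a week throughout, the readings are 100% and 67%. For an arm of 12 with one to four such participants and perfect attendance, they are 12/12 against 11/12 down to 8/12. The documents do not indicate how often this would happen. The effect is confined to the additional per-protocol analysis and the descriptive adherence rate. The intention-to-treat analysis and the sample size are untouched, and the plan itself says that the pilot is not powered for hypothesis testing.

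The judgement would be different if the per-protocol set were the main analysis, or if an adherence threshold decided whether the main trial went ahead. Neither is the case here.

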### 4. RESEARCH PLAN

#### Trial Design

- The pilot study will be single-blind, parallel group, randomized controlled trial of **24 moderate to low functioning** participants randomized in a 1:1 allocation ratio to a high-intensity Resistance Training group (RT) or a Health Education comparator group (HE) for **14 weeks**. We chose the specified population since they are at a greater risk of disability and is often excluded from trials.

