## **Participants**

24 low functioning, both males and females, with 12 participants in each of the treatment arm.

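### Randomization is stratified by gender but the mixed model adjusts only for baseline; if sex predicts change beyond baseline, intervals are wider than the design warrants

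*Combined protocol and SAP*

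**What the plan says.** On allocation, the Randomization paragraph (printed under Temporary Exclusion Criteria) states: "Randomization will be executed via a computer algorithm using random block lengths and stratified by gender". No other stratification factor is named. The Participants section enrols both sexes ("24 low functioning, both males and females, with 12 participants in each of the treatment arm") without giving an expected split.

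On analysis, the Statistical plan states that "we will use a mixed effects model to assess changes in the outcomes with baseline measure serving as covariate". The baseline measure is the only covariate named there or anywhere else. The same section describes the pilot as not powered for hypothesis tests.

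On purpose, the Sample Size paragraph expects that the evaluable participants "would inform variance of the outcomes and feasibility for powering a future large-scale RCT", and the primary objective lists the main study's sample size among the feasibility questions.

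**The concern.** Stratifying by sex (the protocol's gender) removes chance sex imbalance between arms, and with it that part of the sampling variation of the treatment estimate. A model without sex does not know this. It leaves any between-sex variation in the residual, so its standard error describes a less efficient design than the one used. The two-sided interval then covers more often than its nominal level.

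Two things are at stake. With about 20 evaluable people there is little precision to give away. The residual SD is also a product of this study: with and without sex it can differ, and either value misleads if it does not match the model used in the main trial. The plan does not say which SD will be carried forward or whether the main trial will adjust for sex.

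**Working it through.** **Inputs from the documents.** 24 enrolled ("Our goal is to enroll a total of 24 participants"), "randomized in a 1:1 allocation ratio", 20% loss ("Assuming a conservative 20% loss to follow up"), one stratification factor, one covariate.

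**The plan's own figure.** 12 × (1 − 0.20) = 9.6, which rounds to the stated "10 evaluable participants after the 20% loss due to attrition". Two arms give 20 evaluable. The plan states no power, alpha or SD to reproduce.

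**Assumptions (not in the documents).** Blocks of 2 or 4 within sex; two-sided 5% level; 4 of 24 lost at random; 6, 10 or 12 men among the 24; sex effect g beyond baseline of 0, 0.5, 1.0 or 1.5 residual SD; baseline separation d between the sexes of 0, 1 or 2 SD.

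**Expected variance inflation.** With a proportion p of men and residual variance 1, the large-sample residual variance without sex is

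1 + g²·p(1−p) / [1 + d²·p(1−p)].

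The divisor is the part of the sex effect that the baseline covariate already absorbs. For 10 of 24 men, p(1−p) = 0.417 × 0.583 = 0.243.

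- g = 1, d = 0: 1 + 0.243 = 1.243
- g = 1, d = 2: 1 + 0.243/1.972 = 1.123
- g = 0.5, d = 0: 1 + 0.25 × 0.243 = 1.061

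**Simulation.** 6,000 trials per setting with no treatment effect, ANCOVA on baseline with and without sex. Results for 10 men:

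| g | d | Type I error without sex | CI half-width, with ÷ without sex | Residual variance, without ÷ with sex |
|---|---|---|---|---|
| 0 | 0 | 0.053 | 1.012 | 0.998 |
| 0.5 | 0 | 0.046 | 0.980 | 1.066 |
| 1.0 | 0 | 0.032 | 0.900 | 1.263 |
| 1.5 | 0 | 0.022 | 0.801 | 1.591 |
| 0 | 2 | 0.048 | 1.025 | 0.998 |
| 0.5 | 2 | 0.050 | 1.007 | 1.033 |
| 1.0 | 2 | 0.043 | 0.962 | 1.131 |
| 1.5 | 2 | 0.039 | 0.901 | 1.294 |

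The variance ratios agree with the formula apart from small-sample terms. Repeat runs of the g = 1, d = 2 setting gave type I error of 4.7% and 4.8% (Monte Carlo SE about 0.3 points), so that cell is close to nominal.

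Across all 36 settings, the mean estimate without sex stayed within 0.013 SD of zero (no bias), and type I error with sex in the model was 0.044–0.059. Over all sex mixes and separations at g = 1, type I error without sex was 3.2–4.7%, the interval was 3–10% narrower with sex, and residual variance without sex was 12–27% larger.

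**Is stratification the cause?** A second simulation (8,000 runs, equal sexes, 24 analysed, g = 1) gave, without sex, a mean model SE of 0.454 against an empirical SD of 0.422, and coverage of 96.7%; with sex, coverage was 95.2%. With 20 evaluable, coverage without sex was 96.3%. Under unstratified randomization, coverage without sex stayed at 94.7–95.2% (24 analysed, equal sexes). The conservatism therefore comes from stratifying without adjusting.

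**Repeated measures.** A two-visit random-intercept model (10 men, within-person correlation 0.5 or 0.8, g = 1) gave SE ratios with/without sex of 0.89 (d = 0) and 0.95–0.96 (d = 2), and total variance ratios of 1.26–1.27 and 1.13. The single-endpoint results carry over.

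**Consequence for planning.** If a sex-adjusted SD were used to size a main trial that does not adjust for sex, its N would fall short by 1 − 1/1.118 = 11% to 1 − 1/1.272 = 21% at g = 1.

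**Scale.** An SD on 20 − 3 = 17 df has a 95% interval of √(17/χ²), that is 0.75 to 1.50 times the estimate. As SDs, the 12–27% variance differences are √1.118 = 1.06 to √1.272 = 1.13, or 6–13%.

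**The case against.** The strongest reply is about importance. This is a feasibility pilot, the modelled outcomes serve secondary objectives, and no confirmatory test is claimed. The loss is of precision only and depends on a sex effect that the documents do not give. At 0.5 SD it is negligible, and the baseline covariate already absorbs part of any sex effect when the sexes start at different levels. On the SD scale, the 6–13% shift is small beside sampling uncertainty of −25% to +50%. The undersizing figure is a hazard of the remedy: the plan as written produces an unadjusted SD, which suits an unadjusted main trial and errs towards a larger N for an adjusted one. Finally, a short plan that does not mention sex has not excluded it, and the arms themselves are analysed as randomized.

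All of this is fair and limits the weight of the point. It does not remove it. The arms are used; it is the strata that are not. A model that names one covariate should name the other that the design calls for, because leaving it open invites a choice between two models after the data are seen. The undersizing risk is a reason to match the SD to the main trial's model. The no-bias result was shown under random loss only.

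**Conclusion.** The point holds as a conditional statement about precision. Gender is the sole stratification factor and is absent from the stated model. If sex predicts change beyond baseline, the intervals are conservative: at an assumed 1-SD effect they are modestly too wide, and adjustment would narrow them by 3–10%. At 0.5 SD or less there is almost nothing to gain, and the effect becomes material at about 1.5 SD. There is no false-positive inflation, and no bias under random loss. The sizes rest on the assumed sex effect, sex mix, baseline separation, block sizes and 5% level. The change should be made because it is cheap and matches the analysis to the design; the pilot's conclusions do not depend on it.

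**What to change.** In the Statistical plan, name two covariates in the mixed model: the baseline measure and sex, the latter identified as the randomization stratification factor. That is the substantive change.

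As a supporting sentence, add: *Residual SDs will be reported with and without sex, each with a 95% CI; the one that matches the main trial's planned model will be carried forward.*

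The cost is one covariate, one sentence and 1 df, with intervals about 1–2.5% wider if sex does not matter. The sex-adjusted SD must not be used to size a main trial that will not adjust for sex.
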